8.8.3 Clinical Laboratory Evaluation

Urine pregnancy test results will be presented in a by-subject listing.

8.8.4 Other Observations Related to Safety

8.8.4.1 Cutaneous Safety Assessments

Descriptive statistics by treatment group and visit will be provided for dryness and scaling.

8.8.4.2 Local Tolerability Assessments

Descriptive statistics by treatment group and visit will be provided for itching and burning/stinging.

8.8.4.3 Vital Signs

Vital sign measurements include heart rate (HR), sitting blood pressure (BP) (both systolic and diastolic), body temperature, and weight. The data will be summarized with descriptive statistics by visit and treatment group. In addition, the changes from baseline will be summarized with descriptive statistics.

Furthermore, to identify potentially clinically significant vital signs, the following criteria will be used and tabulated as a shift table by visit:

- Systolic Blood Pressure: <90 mmHg (low), 90-140 mmHg (normal), >140 mmHg (high)
- Diastolic Blood Pressure: <90 mm Hg (low), 90-100 mmHg (normal), >100 mmHg (high)

- Heart Rate: <60 beats per minute (low), 60-100 beats per minute (normal), >100 beats per minute (high).

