19.6.1. Vital Sign Measurements

Vital signs as well as changes from Baseline in vital sign measurements will be summarized with descriptive statistics for each treatment group at all applicable study visits.

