xxxxxx	xxxx	xxxxxxxx	xxxxxx	xxxxxxxx	xxxx xxxx xxxxxx xxxxxxxxxxxxxx xxxxxxxxxxxxxxxxxxxxxx xxxxxxxxxx	xxxxxx xxxxxx xxxxxx xxxxxxxxxx xxxxxxxxx xxxx xxxxxx xxxxx xxx xx xxxxxxxxxx xx xxxxx xxxxxxx	
			xxxx xxxxx	xxxxxxxx	xxxx xxxx xxxxxx xxxxxxxxxxxxxx xxxxxxxxxxxxxx xxxxxxxxxxxxxx	xxx xxx xxx xxx xxx xxx	xxx xxxxxxxxx xxx xxxxxxxxx xxx xxxxxxxxx
xxxxxx	xxxx	xxxxxxxx	xxxxxx	xxxxxxxx	xxxx xxxx xxxxxx xxxxxxxxxxxxxx xxxxxxxxxxxxxxxxxxxxxx xxxxxxxxxx	xxxxxx xxxxxx xxxxxx xxxxxxxxxx xxxxxxxxx xxxx xxxxxx xxxxx xxx xx xxxxxxxxxx xx xxxxx xxxxxxx	
			xxxx xxxxx	xxxxxxxx	xxxx xxxx xxxxxx xxxxxxxxxxxxxx xxxxxxxxxxxxxx xxxxxxxxxxxxxx	xxx xxx xxx xxx xxx xxx	xxx xxxxxxxxx xxx xxxxxxxxx xxx xxxxxxxxx

SOURCE: USERNAME\SPONSOR\PROJECT\JOBNAME (DATE, TIME)

Listing sorted by Subject, Visit Number, and Body System (in order presented on eCRF).

Listing 16.2.8.3: Vital Signs
Treatment Arm
(Page xx of yy)

Subject	Age/Sex	Eval	Visit	Date of Assessment	Vital Sign	Result	Units
xxxxxx	xxxx	xxxxxxxx	xxxxxxxx	xxxxxxxx	xxxxxxxx xxxxx xxxxxxxx xxxxx xxxx xxxxxx xxxxxxxxxxxx xxxx xxxxxxxx xxxxx xxxxxxxx xxxxxxxxxxxx xxxxxx	xx xx xxxxx xx xxx xxxx xxx	xxxx xxxxxxxx xx xxxxxxxxxxxx xxxx x xx
			xxxx xxxxx	xxxxxxxx	xxxxxxxx xxxxx xxxxxxxx xxxxx xxxx xxxxxxxxxxxx xxxx xxxxxxxx xxxxx xxxxxxxx xxxxxxxxxxxx	xx xxx xxxx xxx xxx xx	xxxx xxxxxxxx xxxx x
xxxxxx	xxxx	xxxxxxxx	xxxxxxxx	xxxxxxxx	xxxxxxxx xxxxx xxxxxxxx xxxxx xxxx xxxxxx xxxxxxxxxxxx xxxx xxxxxxxx xxxxx xxxxxxxx xxxxxxxxxxxx xxxxxx	xx xx xxx xx xx xx xxx	xxxx xxxxxxxx xx xxxxxxxxxxxx xxxx x xx
			xxxx xxxxx	xxxxxxxx	xxxxxxxx xxxxx xxxxxxxx xxxxx xxxx xxxxxxxxxxxx xxxx xxxxxxxx xxxxx xxxxxxxx xxxxxxxxxxxx	xxx xxxx xxx xxxx xxx xxxx xxx xxxx xxx xxxx	

SOURCE: USERNAME\SPONSOR\PROJECT\JOBNAME (DATE, TIME)

Listing sorted by Subject, Visit Number, and Vital Sign (in alphabetical order).

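### The SAP labels every diastolic reading below 90 mmHg low, so the vital-signs shift table cannot show a diastolic fall from any baseline under 90

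*SAP*

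**What the plan says.** SAP section 8.8.4.3 plans descriptive statistics for vital signs by visit and for change from Baseline. It then adds a categorical display, introduced as follows: "to identify potentially clinically significant vital signs, the following criteria will be used and tabulated as a shift table by visit". The two blood-pressure definitions are:

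- "Systolic Blood Pressure: <90 mmHg (low), 90-140 mmHg (normal), >140 mmHg (high")
- "Diastolic Blood Pressure: <90 mm Hg (low), 90-100 mmHg (normal), >100 mmHg (high")

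The shell of Table 14.3.1.4.2 carries the same three diastolic bands (<90, 90-100, >100 mmHg) as rows for Baseline and columns for Week 12. It prints the ranges without the words low, normal or high. SAP section 10, which lists departures from the protocol's analyses, does not mention these limits, and nothing elsewhere in either document gives another diastolic limit or a reason for this one.

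Protocol section 19.6.1 asks for less: "Vital signs as well as changes from Baseline in vital sign measurements will be summarized with descriptive statistics for each treatment group". The shift table is therefore an addition made by the SAP.

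**The concern.** A shift table built to pick out notable values needs a lowest category that separates low readings from ordinary ones. Here the lowest diastolic category starts at the systolic limit and takes in everything beneath it. A patient at 80 and a patient at 50 mmHg are classified alike, and a patient who moves from the first value to the second is recorded as unchanged.

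At stake is the only categorical blood-pressure output in the plan. For patients who start below 90 mmHg it would register rises but never falls. A reader who saw almost no downward diastolic shifts could take that as reassurance, when the bands had ruled such shifts out for those patients.

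**Working it through.** There is no sample size, power or test statistic to reproduce. The check applies the SAP's own limits.

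**Inputs.** From SAP 8.8.4.3: systolic S is normal for 90 ≤ S ≤ 140; diastolic D is low for D < 90, normal for 90 ≤ D ≤ 100 and high for D > 100. The one fact added is that diastolic is below systolic.

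**Step 1: do the two sets of limits fit together?** For D to be normal, the gap S − D must lie between S − 100 and S − 90.

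| Systolic (all normal by the SAP) | Gap needed for a normal diastolic |
|---|---|
| 90 | −10 to 0: impossible |
| 100 | 0 to 10 mmHg |
| 120 | 20 to 30 mmHg |
| 140 | 40 to 50 mmHg |

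Readings of 120/80, 110/70, 90/60 and 140/85 are each normal on systolic and low on diastolic. At the bottom of the normal systolic band, no diastolic can be normal.

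**Step 2: what can the shift table register?** Take every whole-number diastolic baseline b from 30 to 89 and every lower follow-up value down to 20. The number of falls is the sum of (b − 20), that is 10 + 11 + … + 69 = 60 × (10 + 69) / 2 = 2,370. Both values are below 90 in every pair, so all 2,370 stay in the <90 to <90 cell and none registers as a shift. Examples:

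- 85 to 45 and 75 to 50: low to low, no shift.
- 95 to 85 and 95 to 45: both normal to low, in the same cell.
- 75 to 92: low to normal, shown as an upward shift.

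**Step 3: how many patients might this cover?** The documents give no diastolic distribution, so this step is illustration only. Assume normal readings with mean 70-85 and SD 8-12 mmHg.

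- Share below 90: lowest Φ((90 − 85)/12) = 0.662, highest Φ((90 − 70)/8) = 0.994.
- Share in 90-100: from 0.006 (mean 70, SD 8) to 0.242 (mean 85, SD 10).
- Share in the single <90 to <90 cell, if Baseline and Week 12 have the same distribution with correlation 0.5: from 0.510 (mean 85, SD 12) to 0.988 (mean 70, SD 8).

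The correlation is also an assumption. With none, the low end is 0.662² = 0.438; with perfect correlation it is 0.662. The high end moves only between 0.994² = 0.988 and 0.994.

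**The case against.** The strongest reply is that little is lost.

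- The protocol's safety endpoints are adverse events and the cutaneous and local tolerability scores. Vital signs enter only through SAP section 7.2, and the protocol never asked for a shift table.
- The study flow chart schedules the physical examination, which includes vital signs, only at Baseline and Week 12. This is therefore one block of one two-visit table.
- Table 14.3.1.4.1 gives the diastolic mean, SD, median and range at each visit and for the change. Listing 16.2.8.3 shows each patient's values. A clinically important fall could also be recorded as an adverse event under protocol section 17.2.
- The shell prints no labels, so no output would call 120/80 low.

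All of this stands, and it limits the importance of the point. None of it repairs the table. Means, ranges and listings do not count patients with low diastolic values, and leaving the words out of the shell does not supply the missing lower band.

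Two further replies are partly right. First, no shift table can show a fall within its lowest band, and that applies equally to systolic below 90 and heart rate below 60. The difference is how much the diastolic band contains. Second, the documents state no diastolic reference range, so calling readings below 90 ordinary draws on general knowledge, and a pair such as 120/95 is normal on both scales. But the mismatch at systolic 90 follows from the SAP's own limits, and the narrow gaps needed at 100 and 120 point the same way. The percentages in Step 3 are soft, and the conclusion does not depend on them.

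**Conclusion.** The limits are wrong as written. The diastolic and systolic lower limits coincide, the text and the shell agree on the faulty bands, and the resulting table cannot do the job SAP 8.8.4.3 gives it for low diastolic values. That follows from the cut-points alone: no fall from a baseline below 90 can register.

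How many patients this covers rests on assumption. With the means and SDs assumed above and a correlation of 0.5, between about half and nearly all patients (51-99%) would sit in one uninformative cell.

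The consequence is contained. It affects one descriptive safety table, with the underlying values kept elsewhere. Efficacy endpoints, analysis populations, type I error and power are untouched. It is a definition error that should be corrected before unblinding, and it does not threaten the trial's conclusions.

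**What to change.** Revise the diastolic line in SAP 8.8.4.3 and the diastolic block of the Table 14.3.1.4.2 shell together, so that the limits agree with the systolic limits and the lowest band no longer holds ordinary readings. The sponsor's medical lead should set the values; none is proposed here. Do this before the blind is broken, which SAP section 2 allows for, so that safety cut-points are not chosen with results in view.

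The cost is one line of text and one block of one shell, with no change to data collection or efficacy analysis. In the same edit, correct the heart-rate rows of that shell, which are labelled in mmHg under column heads in beats per minute.

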8.8.4.4 Physical Examination

Abnormal physical examination findings will be summarized by body system, visit, and treatment group. In addition to the summary, all physical examination findings will be listed.

8.8.4.5 Patient Global Impression of Treatment Side-Effects (PGI-SE)

Descriptive statistics by treatment group and visit will be provided for PGI-SE.

9. DETERMINATION OF SAMPLE SIZE

The following power calculations are based on the observed Week 12 results of the Phase 2 study, SGT-EBP01-09. This study was a three-arm trial including E-BPO cream, 1% and 5%, and vehicle in the treatment of rosacea. Estimates from the E-BPO cream, 5% arm were used in the power assessments. The anticipated randomization ratio is 2:1 for E-BPO cream, 5% and vehicle, respectively. The computations were performed with nQuery Advisor Version 7.0 using a two-sided test with a statistical significance value of 0.05.

A sample size of 86 in the E-BPO cream, 5% and 43 in the vehicle group has 95% power to detect a statistically significant difference in the proportion of patients who have at least a 2-grade reduction at Week 12 from Baseline in IGA and are clear or almost clear. The estimated percentages with a 2-grade reduction at Week 12 from Baseline in the IGA and clear or almost clear are 53.3% and 20.0% for the E-BPO cream and vehicle, respectively.

A sample size of 200 in the E-BPO cream, 5% and 100 in the vehicle group has 95% power to detect a statistically significant difference in inflammatory lesions. The estimated absolute change from Baseline in treatment means were -14.1 and -7.4 for E-BPO cream and vehicle, respectively, with a standard deviation (SD) of 6.70 and 17.24, respectively.

The sample sizes above will be increased to give a planned enrollment of 234 in the E-BPO cream, 5% group and 117 in the vehicle group since the Phase 3 trial is expected to enroll patients who are as a group more severe than those of the Phase 2 trial. This is a consequence of some changes in the inclusion criteria.

10. CHANGES IN THE PLANNED ANALYSES

There are no changes in the conduct of the study, but there are minor changes to the planned analyses.

Due to feedback received, the primary efficacy analysis was adjusted back to the original analysis. The modification to only use the non-parametric version as described in v4 of the protocol was not accepted by the agency. The original approach uses an ANCOVA analysis with the terms for treatment, analysis center, and Baseline count (and treatment-by-center interaction if the term is significant at 0.10). If the two-sided p-value for the skewness test is significant at 0.01, then the rank-transformed data will be used instead of nominal values. The original approach was accepted by the agency.

The pooling analysis described in the protocol is updated in the statistical analysis plan (SAP) to reflect the intended analysis. The protocol discusses pooling sites with five or fewer subjects enrolled in each treatment arm. Taking into consideration the randomization ratio, the SAP requires ten subjects in the active treatment arm and five subjects in the vehicle group.

As part of the pooling analysis, the treatment effect within investigational site must be investigated. The protocol states the site main effect will be examined by using a one-way analysis of variance (for lesion count variables) or a logistic regression analysis (for dichotomized IGA) with a factor of site. The SAP instead explains site will be incorporated into the primary analysis models. Change from Baseline in lesion counts will be analyzed with an ANCOVA (unranked or ranked) with factors of treatment group, investigational site and treatment group by investigational site interaction, and the respective Baseline lesion count variable as a covariate. The dichotomized primary endpoint will be analyzed with a logistic regression with factors of treatment group, investigational site and the interaction term of treatment group by investigational site.

The protocol describes repeated measures sensitivity analyses for the primary efficacy endpoints. Treatment group, analysis center and visit are listed as factors for the repeated measures analyses. In addition to these factors, the SAP includes a factor of treatment group by visit interaction.

The protocol describes imputing only Week 12 data with MCMC imputation, but all missing post-baseline data will be imputed. Only 2 seeds are needed for the MCMC imputation for inflammatory lesions (one seed for S5G4T-1 and one seed for vehicle) instead of the 6 seeds that are given in the protocol. Only 2 seeds are needed for the MCMC imputation for IGA (one seed for S5G4T-1 and one seed for vehicle) so only one seed was given in the SAP. Using only the Week 12 seed addresses concern from the FDA with regard to imputing data at each visit as the multiple seeds in the protocol suggests. Only one seed is needed for treatment group as PROC MI will impute data across the visits.

All seeds given in the SAP were produced in SAS as seeds given in the 54-02 protocol were identical to the 54-01 study protocol.

Geographic region was removed from the examination of subgroups as all sites in the study are in the United States.

Table 14.2.15.1: Summary of RosaQoL Questionnaire Responses at Baseline and Week 12 (Intent-to-Treat Population)	117
Table 14.2.15.2: Summary of RosaQoL Questionnaire Responses at Baseline and Week 12 (Per-Protocol Population)	121
Table 14.3.0.1: Summary of Extent of Exposure (Safety Population)	122
Table 14.3.1.1: Summary of Cutaneous Safety and Tolerability Evaluations (Safety Population).....	123
Table 14.3.1.2.1: Summary of Treatment-Emergent Adverse Event Characteristics (Safety Population).....	131
Table 14.3.1.2.2: Summary of Treatment-Emergent Adverse Events by MedDRA System Organ Class and Preferred Term (Safety Population).....	133
Table 14.3.1.2.3: Summary of Treatment-Emergent Adverse Events by Severity (Safety Population)	134
Table 14.3.1.2.4: Summary of Treatment-Emergent Adverse Events by Relationship to Study Drug (Safety Population)	135
Table 14.3.1.3.1: Summary of Treatment-Emergent Serious Adverse Event Characteristics (Safety Population).....	136
Table 14.3.1.3.2: Summary of Treatment-Emergent Serious Adverse Events by MedDRA System Organ Class and Preferred Term (Safety Population).....	138
Table 14.3.1.3.3: Summary of Serious Treatment-Emergent Adverse Events by Severity (Safety Population)	139
Table 14.3.1.3.4: Summary of Treatment-Emergent Serious Adverse Events by Relationship to Study Drug (Safety Population).....	140
Table 14.3.1.4.1: Summary of Vital Signs (Safety Population)	141
Table 14.3.1.4.2: Shift Table of Vital Signs (Safety Population).....	146

Statistical Analysis Plan

Sol-Gel Technologies Ltd. SGT-54-02

Version: 1.0

Date: 02 MAY 2019

Table 14.3.1.5: Summary of Abnormal Physical Examination Findings by Visit (Safety Population)147

Table 14.3.1.6: Summary of Patient Global Impression of Treatment Side-Effects (PGI-SE) at Each Evaluation (Safety Population)148

Table 14.0.1: Summary of Subject Completion/Discontinuation
(All Randomized Subjects)

	E-BPO 5% Cream (N=xxx)	Vehicle Cream (N=xxx)	Total (N=xxx)
Completed Study			
Yes	xx (xx.x%)	xx (xx.x%)	xx (xx.x%)
No	xx (xx.x%)	xx (xx.x%)	xx (xx.x%)
Reason for Discontinuation			
Adverse Event	xx (xx.x%)	xx (xx.x%)	xx (xx.x%)
Lost to Follow-Up	xx (xx.x%)	xx (xx.x%)	xx (xx.x%)
Lack of Efficacy	xx (xx.x%)	xx (xx.x%)	xx (xx.x%)
Pregnancy	xx (xx.x%)	xx (xx.x%)	xx (xx.x%)
Protocol Violation	xx (xx.x%)	xx (xx.x%)	xx (xx.x%)
Withdrawal by Subject	xx (xx.x%)	xx (xx.x%)	xx (xx.x%)
Study Terminated by Sponsor	xx (xx.x%)	xx (xx.x%)	xx (xx.x%)
Physician Decision	xx (xx.x%)	xx (xx.x%)	xx (xx.x%)
Worsening of Condition	xx (xx.x%)	xx (xx.x%)	xx (xx.x%)
Other	xx (xx.x%)	xx (xx.x%)	xx (xx.x%)

SOURCE: USERNAME\SPONSOR\PROJECT\JOBNAME (DATE,TIME)

Table 14.0.2.1: Summary of Subject Enrollment and Evaluability
(All Randomized Subjects)

	E-BPO 5% Cream (N=xxx)	Vehicle Cream (N=xxx)	Total (N=xxx)
Number of Randomized Subjects	xx	xx	xx
Number of Subjects Included in the ITT Population	xx (xx.x%)	xx (xx.x%)	xx (xx.x%)
Number of Subjects Excluded from the ITT Population	xx (xx.x%)	xx (xx.x%)	xx (xx.x%)
Reason Excluded from the ITT Population			
Not Dispensed Study Drug	xx (xx.x%)	xx (xx.x%)	xx (xx.x%)
Number of Subjects Included in the Safety Population	xx (xx.x%)	xx (xx.x%)	xx (xx.x%)
Number of Subjects Excluded from the Safety Population	xx (xx.x%)	xx (xx.x%)	xx (xx.x%)
Reasons Excluded from the Safety Population ^a			
No Documented use of Study Drug	xx (xx.x%)	xx (xx.x%)	xx (xx.x%)
No Post Baseline Safety Assessment	xx (xx.x%)	xx (xx.x%)	xx (xx.x%)
Number of Subjects Included in the PP Population	xx (xx.x%)	xx (xx.x%)	xx (xx.x%)
Number of Subjects Excluded from the PP Population	xx (xx.x%)	xx (xx.x%)	xx (xx.x%)
Reasons Excluded from the PP Population ^a			
Not Included in ITT Population	xx (xx.x%)	xx (xx.x%)	xx (xx.x%)
Violated Inclusion/Exclusion Criteria	xx (xx.x%)	xx (xx.x%)	xx (xx.x%)
Used Interfering Concomitant Medication	xx (xx.x%)	xx (xx.x%)	xx (xx.x%)
Did not Attend Week 12/ET Visit	xx (xx.x%)	xx (xx.x%)	xx (xx.x%)
Missed More Than 1 Post-Baseline Visit Prior to Week 12	xx (xx.x%)	xx (xx.x%)	xx (xx.x%)
Not Compliant with Dosing Regimen ^b	xx (xx.x%)	xx (xx.x%)	xx (xx.x%)
Week 12/ET Visit Out of Window (+/-4 days)	xx (xx.x%)	xx (xx.x%)	xx (xx.x%)
Other	xx (xx.x%)	xx (xx.x%)	xx (xx.x%)

^a Table includes primary reason (assigned in order presented in table) for reason subject was excluded.

^b Subjects lost to follow-up not included. A subject was considered compliant with the dosing regimen if the subject applied 80-120% of the expected number of applications and did not miss more than 5 consecutive applications while enrolled in the study.

SOURCE: USERNAME\SPONSOR\PROJECT\JOBNAME (DATE,TIME)

Table 14.0.2.2: Summary of Subject Evaluability by Analysis Center and Investigational Site
 (All Randomized Subjects)
 (Page 1 of xx)

Analysis Center	Investigational Site	Number Randomized	E-BPO 5% Cream			Vehicle Cream		
			ITT	PP	Safety	ITT	PP	Safety
xx	xx	xx	xx	xx	xx	xx	xx	xx
xx	xx	xx	xx	xx	xx	xx	xx	xx
	xx	xx	xx	xx	xx	xx	xx	xx
xx	xx	xx	xx	xx	xx	xx	xx	xx
xx	xx	xx	xx	xx	xx	xx	xx	xx
	xx	xx	xx	xx	xx	xx	xx	xx
	xx	xx	xx	xx	xx	xx	xx	xx

SOURCE: USERNAME\SPONSOR\PROJECT\JOBNAME (DATE,TIME)

Table 14.1.1.1: Summary of Subject Demographic Characteristics
(Intent-to-Treat Population)
(Page 1 of 2)

	E-BPO 5% Cream (N=xxx)	Vehicle Cream (N=xxx)	Total (N=xxx)
Age (years)			
n	xx	xx	xx
Mean	xx.x	xx.x	xx.x
SD	xx.xx	xx.xx	xx.xx
Median	xx.x	xx.x	xx.x
Min. to Max.	xx to xx	xx to xx	xx to xx
< Median (xx years)	xx (xx.x%)	xx (xx.x%)	xx (xx.x%)
≥ Median (xx years)	xx (xx.x%)	xx (xx.x%)	xx (xx.x%)
Sex			
n	xx	xx	xx
Male	xx (xx.x%)	xx (xx.x%)	xx (xx.x%)
Female	xx (xx.x%)	xx (xx.x%)	xx (xx.x%)
Ethnicity			
n	xx	xx	xx
Hispanic or Latino	xx (xx.x%)	xx (xx.x%)	xx (xx.x%)
Not Hispanic or Latino	xx (xx.x%)	xx (xx.x%)	xx (xx.x%)
Not Reported/Unknown	xx (xx.x%)	xx (xx.x%)	xx (xx.x%)

^a See Listing 16.2.4.1 for a complete list of other races.

SOURCE: USERNAME\SPONSOR\PROJECT\JOBNAME (DATE,TIME)

Table 14.1.1.1: Summary of Subject Demographics
(Intent-to-Treat Population)
(Page 2 of 2)

	E-BPO 5% Cream (N=xxx)	Vehicle Cream (N=xxx)	Total (N=xxx)
Race			
n	xx	xx	xx
American Indian or Alaska Native	xx (xx.x%)	xx (xx.x%)	xx (xx.x%)
Asian	xx (xx.x%)	xx (xx.x%)	xx (xx.x%)
Black or African American	xx (xx.x%)	xx (xx.x%)	xx (xx.x%)
Native Hawaiian or Other Pacific Islander	xx (xx.x%)	xx (xx.x%)	xx (xx.x%)
White	xx (xx.x%)	xx (xx.x%)	xx (xx.x%)
Multiple/Other ^a	xx (xx.x%)	xx (xx.x%)	xx (xx.x%)

^a See Listing 16.2.4.1 for a complete list of other races.

SOURCE: USERNAME\SPONSOR\PROJECT\JOBNAME (DATE,TIME)

Repeat Table 14.1.1.1 for the following tables:

Table 14.1.1.2: Summary of Subject Demographics (Per-Protocol Population)

Table 14.1.1.3: Summary of Subject Demographics (Safety Population)

Table 14.1.2.1: Subject Baseline Characteristics
(Intent-to-Treat Population)
(Page 1 of 2)

	E-BPO 5% Cream (N=xxx)	Vehicle Cream (N=xxx)	Total (N=xxx)
Height (cm)			
n	xx	xx	xx
Mean	xx.x	xx.x	xx.x
SD	xx.xx	xx.xx	xx.xx
Median	xx.x	xx.x	xx.x
Min. to Max.	xx to xx	xx to xx	xx to xx
Weight (kg)			
n	xx	xx	xx
Mean	xx.x	xx.x	xx.x
SD	xx.xx	xx.xx	xx.xx
Median	xx.x	xx.x	xx.x
Min. to Max.	xx to xx	xx to xx	xx to xx
BMI (kg/m²)			
n	xx	xx	xx
Mean	xx.x	xx.x	xx.x
SD	xx.xx	xx.xx	xx.xx
Median	xx.x	xx.x	xx.x
Min. to Max.	xx to xx	xx to xx	xx to xx

SOURCE: USERNAME\SPONSOR\PROJECT\JOBNAME (DATE,TIME)

Table 14.1.2.1: Subject Baseline Characteristics
(Intent-to-Treat Population)
(Page 2 of 2)

	E-BPO 5% Cream (N=xxx)	Vehicle Cream (N=xxx)	Total (N=xxx)
Inflammatory Lesion Count			
n	xx	xx	xx
Mean	xx.x	xx.x	xx.x
SD	xx.xx	xx.xx	xx.xx
Median	xx.x	xx.x	xx.x
Min. to Max.	xx to xx	xx to xx	xx to xx
Investigator Global Assessment			
n	xx	xx	xx
0 - Clear	xx (xx.x%)	xx (xx.x%)	xx (xx.x%)
1 – Almost Clear	xx (xx.x%)	xx (xx.x%)	xx (xx.x%)
2 - Mild	xx (xx.x%)	xx (xx.x%)	xx (xx.x%)
3 - Moderate	xx (xx.x%)	xx (xx.x%)	xx (xx.x%)
4 - Severe	xx (xx.x%)	xx (xx.x%)	xx (xx.x%)

SOURCE: USERNAME\SPONSOR\PROJECT\JOBNAME (DATE,TIME)

Repeat Table 14.1.2.1 for the following table:

Table 14.1.2.2: Subject Baseline Characteristics (Per-Protocol Population)

Table 14.1.2.3: Subject Baseline Characteristics (Safety Population)

Table 14.1.3.1: Summary of Medical History by System Organ Class and Preferred Term
 (Intent-to-Treat Population)
 (Page 1 of xx)

System Organ Class Preferred Term	E-BPO 5% Cream (N=xxx)		Vehicle Cream (N=xxx)		Total (N=xxx)	
	By Subject ^a	By Event ^b	By Subject ^a	By Event ^b	By Subject ^a	By Event ^b
Number (%) of Subjects Reporting at Least One Medical History Term	xx (xx.x%)	xx	xx (xx.x%)	xx	xx (xx.x%)	xx
System Organ Class	xx (xx.x%)	xx	xx (xx.x%)	xx	xx (xx.x%)	xx
Preferred Term	xx (xx.x%)	xx	xx (xx.x%)	xx	xx (xx.x%)	xx

^a Counts reflect number of subjects reporting one or more medical history terms that map to MedDRA. At each level of summarization (System Organ Class or Preferred Term) subjects are counted once. Percentages are based on the number of subjects in the safety population.

^b Counts reflect number of medical history terms that map to MedDRA.

Note: MedDRA Version 21.0

SOURCE: USERNAME\SPONSOR\PROJECT\JOBNAME (DATE,TIME)

{NOTE TO PROGRAMMER: The table will be sorted by overall descending frequency of SOC and then, within a SOC, by overall descending frequency of PT}

Repeat Table 14.1.3.1 for the following table:

Table 14.1.3.2: Summary of Medical History by System Organ Class and Preferred Term (Per-Protocol Population)

Table 14.1.3.3: Summary of Medical History by System Organ Class and Preferred Term (Safety Population)

Table 14.1.4.1: Summary of Prior Medications by ATC Level 2 and Preferred Name
 (Safety Population)
 (Page 1 of xx)

ATC Level 2 Term ^a Preferred Name	E-BPO 5% Cream (N=xxx)	Vehicle Cream (N=xxx)
Number (%) of Subjects Reporting at Least One Prior Medication	xx (xx.x%)	xx (xx.x%)
ATC Level 2 Term	xx (xx.x%)	xx (xx.x%)
Preferred Name	xx (xx.x%)	xx (xx.x%)

^a Counts reflect number of subjects reporting one or more medications that map to the WHO term. At each level of summarization (ATC Level 2 Term or Preferred Name) subjects are counted once. Percentages are based on the number of subjects in the safety population.

Note: WHO Drug Global Dictionary, Format B3, Version March 1, 2018
 Prior medications are those used before the date of first study drug application.

SOURCE: USERNAME\SPONSOR\PROJECT\JOBNAME (DATE,TIME)

Table 14.1.4.2: Summary of Concomitant Medications by ATC Level 2 and Preferred Name
(Safety Population)
(Page 1 of xx)

ATC Level 2 Term ^a Preferred Name	E-BPO 5% Cream (N=xxx)	Vehicle Cream (N=xxx)
Number (%) of Subjects Reporting at Least One Concomitant Medication	xx (xx.x%)	xx (xx.x%)
ATC Level 2 Term Preferred Name	xx (xx.x%) xx (xx.x%)	xx (xx.x%) xx (xx.x%)

^a Counts reflect number of subjects reporting one or more medications that map to the WHO term. At each level of summarization (ATC Level 2 Term or Preferred Name) subjects are counted once. Percentages are based on the number of subjects in the safety population.

Note: WHO Drug Global Dictionary, Format B3, Version March 1, 2018
Concomitant medications are those used on/after the date of first study drug application.

SOURCE: USERNAME\SPONSOR\PROJECT\JOBNAME (DATE,TIME)

Table 14.2.1.1: Pooling Analysis for Primacy Efficacy Endpoints
(Intent-to-Treat Population)

Endpoint	Investigational Site Pooling Analysis		Analysis Center Pooling Analysis	
	Skewness P-Value	Investigational Site by Treatment Group P-Value	Skewness P-Value	Analysis Center Treatment Group P-Value
Absolute Change from Baseline in Inflammatory Lesion Counts at Week 12	x.xxx ^c			
Ranked Analysis		x.xxx ^a		x.xxx ^e
Unranked Analysis		x.xxx ^b		x.xxx ^f
Achieving Clear or Almost Clear at Week 12	NA	x.xxx ^d	NA	x.xxx ^g

^a P-value for the interaction term from a ranked analysis of covariance with factors of treatment, investigational site, treatment by investigational site interaction and Baseline lesion count as a covariate.

^b P-value for the interaction term from an unranked analysis of covariance with factors of treatment, investigational site, treatment by investigational site interaction and Baseline lesion count as a covariate.

^c Skewness test, based on methods presented by J.H. Zar (1984), assessed for each imputed dataset. The average p-value is presented.

^d P-value for the interaction term from a logistic regression with factors of treatment, investigational site, treatment by investigational site interaction.

^e P-value for the interaction term from a ranked analysis of covariance with factors of treatment, analysis center, treatment by analysis center interaction and Baseline lesion count as a covariate.

^f P-value for the interaction term from an unranked analysis of covariance with factors of treatment, analysis center, treatment by analysis center interaction and Baseline lesion count as a covariate.

^g P-value for the interaction term from a logistic regression with factors of treatment, analysis center, treatment by analysis center interaction.

Note: Multiple imputation (MCMC) used to impute missing values.

SOURCE: USERNAME/SPONSOR/PROJECT/JOBNAME (DATE,TIME)

{NOTE TO PROGRAMMER: ADJUST FOOTNOTE “d” AND/OR “g” IF FIRTH’S PENALIZED LIKELIHOOD IS NEEDED}

Table 14.2.1.2: Primary Efficacy Analysis: Absolute Change from Baseline in Inflammatory Lesion Count and Dichotomized IGA Success at Week 12 (Intent-to-Treat Population)

	E-BPO 5% Cream (N=xxx)	Vehicle Cream (N=xxx)	Skewness P-Value	Treatment P-Value
Inflammatory Lesion Count – Absolute Change from Baseline				
LSMean ^a	xx.x	xx.x	x.xxx ^b	x.xxx ^a
LSSD ^a	xx.xx	xx.xx		x.xxx ^c
Achieving Clear or Almost Clear				
Success	xx.x%	xx.x%	N/A	x.xxx ^d
Failure	xx.x%	xx.x%		

^a Least squares means, standard deviations and treatment p-value from an analysis of covariance with factors of treatment group and analysis center and Baseline lesion count as a covariate. Negative least squares means values represent decrease from Baseline.

^b Skewness test, based on methods presented by J.H. Zar (1984), assessed for each imputed dataset. The average p-value is presented.

^c P-value from a ranked analysis of covariance with factors of treatment group and analysis center and Baseline lesion count as a covariate.

^d P-value from a logistic regression with factors of treatment group and analysis center.

Note: Multiple imputation (MCMC) used to impute missing values.

SOURCE: USERNAME\SPONSOR\PROJECT\JOBNAME (DATE, TIME)

{NOTE TO PROGRAMMER: ADJUST FOOTNOTE “d” IF FIRTH’S PENALIZED LIKELIHOOD IS NEEDED}

Repeat Table 14.2.1.2 for the following table:

Table 14.2.1.3: Primary Efficacy Analysis: Absolute Change from Baseline in Inflammatory Lesion Count and Dichotomized IGA Success at Week 12 (Per-Protocol Population)

Update footnote to “Note: Missing values imputed using last observation carried forward.”

Table 14.2.2.1.1: Summary of Inflammatory Lesion Counts at Each Evaluation
(Intent-to-Treat Population)
(Page 1 of 4)

Inflammatory Lesion Counts	E-BPO 5% Cream (N=xxx)	Vehicle Cream (N=xxx)
Baseline		
n	xx	xx
Mean	xx.x	xx.x
SD	xx.xx	xx.xx
Median	xx.x	xx.x
Min. to Max.	xx to xx	xx to xx
Week 2		
n	xx	xx
Mean	xx.x	xx.x
SD	xx.xx	xx.xx
Median	xx.x	xx.x
Min. to Max.	xx to xx	xx to xx
Change from Baseline		
n	xx	xx
Mean	xx.x	xx.x
SD	xx.xx	xx.xx
Median	xx.x	xx.x
Min. to Max.	xx to xx	xx to xx
Percent Change from Baseline		
n	xx	xx
Mean	xx.x	xx.x
SD	xx.xx	xx.xx
Median	xx.x	xx.x
Min. to Max.	xx to xx	xx to xx

Note: Multiple imputation (MCMC) used to impute missing values. Summary statistics for Weeks 2, 4, 8, and 12 represent average values, obtained from averaging the summary statistics generated from each imputed dataset.

SOURCE: USERNAME\SPONSOR\PROJECT\JOBNAME (DATE,TIME)

Table 14.2.2.1.1: Summary of Inflammatory Lesion Counts at Each Evaluation
(Intent-to-Treat Population)
(Page 2 of 4)

Inflammatory Lesion Counts	E-BPO 5% Cream (N=xxx)	Vehicle Cream (N=xxx)
Week 4		
n	xx	xx
Mean	xx.x	xx.x
SD	xx.xx	xx.xx
Median	xx.x	xx.x
Min. to Max.	xx to xx	xx to xx
 Change from Baseline		
n	xx	xx
Mean	xx.x	xx.x
SD	xx.xx	xx.xx
Median	xx.x	xx.x
Min. to Max.	xx to xx	xx to xx
 Percent Change from Baseline		
n	xx	xx
Mean	xx.x	xx.x
SD	xx.xx	xx.xx
Median	xx.x	xx.x
Min. to Max.	xx to xx	xx to xx

Note: Multiple imputation (MCMC) used to impute missing values. Summary statistics for Weeks 2, 4, 8, and 12 represent average values, obtained from averaging the summary statistics generated from each imputed dataset.

SOURCE: USERNAME/SPONSOR/PROJECT/JOBNAME (DATE,TIME)

Table 14.2.2.1.1: Summary of Inflammatory Lesion Counts at Each Evaluation
(Intent-to-Treat Population)
(Page 2 of 4)

Inflammatory Lesion Counts	E-BPO 5% Cream (N=xxx)	Vehicle Cream (N=xxx)
Week 8		
n	xx	xx
Mean	xx.x	xx.x
SD	xx.xx	xx.xx
Median	xx.x	xx.x
Min. to Max.	xx to xx	xx to xx
Change from Baseline		
n	xx	xx
Mean	xx.x	xx.x
SD	xx.xx	xx.xx
Median	xx.x	xx.x
Min. to Max.	xx to xx	xx to xx
Percent Change from Baseline		
n	xx	xx
Mean	xx.x	xx.x
SD	xx.xx	xx.xx
Median	xx.x	xx.x
Min. to Max.	xx to xx	xx to xx

Note: Multiple imputation (MCMC) used to impute missing values. Summary statistics for Weeks 2, 4, 8, and 12 represent average values, obtained from averaging the summary statistics generated from each imputed dataset.

SOURCE: USERNAME/SPONSOR/PROJECT/JOBNAME (DATE,TIME)

Table 14.2.2.1.1: Summary of Inflammatory Lesion Counts at Each Evaluation
(Intent-to-Treat Population)
(Page 4 of 4)

Inflammatory Lesion Counts	E-BPO 5% Cream (N=xxx)	Vehicle Cream (N=xxx)
Week 12		
n	xx	xx
Mean	xx.x	xx.x
SD	xx.xx	xx.xx
Median	xx.x	xx.x
Min. to Max.	xx to xx	xx to xx
Change from Baseline		
n	xx	xx
Mean	xx.x	xx.x
SD	xx.xx	xx.xx
Median	xx.x	xx.x
Min. to Max.	xx to xx	xx to xx
Percent Change from Baseline		
n	xx	xx
Mean	xx.x	xx.x
SD	xx.xx	xx.xx
Median	xx.x	xx.x
Min. to Max.	xx to xx	xx to xx

Note: Multiple imputation (MCMC) used to impute missing values. Summary statistics for Weeks 2, 4, 8, and 12 represent average values, obtained from averaging the summary statistics generated from each imputed dataset. Negative values represent decrease from Baseline.

SOURCE: USERNAME/SPONSOR/PROJECT\JOBNAME (DATE,TIME)

Repeat Table 14.2.2.1.1 for the following table:

Table 14.2.2.1.2: Summary of Inflammatory Lesion Counts at Each Evaluation (Per-Protocol Population)

Change footnote to “Note: Missing values imputed using last observation carried forward. Negative values represent decrease from Baseline.”

Table 14.2.2.2: Summary of Absolute Change in Inflammatory Lesion Counts at Week 12 by Analysis Center
(Intent-to-Treat Population)

Analysis Center (Investigational Sites)	E-BPO 5% Cream (N=xxx)			Vehicle Cream (N=xxx)		
	n	Mean	SD	n	Mean	SD
xx (y, z)	xx	xx.x	xx.xx	xx	xx.x	xx.xx
xx (y, z)	xx	xx.x	xx.xx	xx	xx.x	xx.xx
xx (y, z)	xx	xx.x	xx.xx	xx	xx.x	xx.xx
xx (y, z)	xx	xx.x	xx.xx	xx	xx.x	xx.xx
xx (y, z)	xx	xx.x	xx.xx	xx	xx.x	xx.xx
xx (y, z)	xx	xx.x	xx.xx	xx	xx.x	xx.xx
xx (y, z)	xx	xx.x	xx.xx	xx	xx.x	xx.xx
xx (y, z)	xx	xx.x	xx.xx	xx	xx.x	xx.xx
xx (y, z)	xx	xx.x	xx.xx	xx	xx.x	xx.xx

Note: Multiple imputation (MCMC) used to impute missing values. Summary statistics represent average values, obtained from averaging the summary statistics generated from each imputed dataset. Negative values represent decrease from Baseline.

SOURCE: USERNAME\SPONSOR\PROJECT\JOBNAME (DATE, TIME)

Table 14.2.3.1.1: Summary of Investigator Global Assessment at Each Evaluation
(Intent-to-Treat Population)
(Page 1 of 4)

Investigator Global Assessment	E-BPO 5% Cream (N=xxx)	Vehicle Cream (N=xxx)
Baseline		
n	xx	xx
0 - Clear	xx (xx.x%)	xx (xx.x%)
1 - Almost Clear	xx (xx.x%)	xx (xx.x%)
2 - Mild	xx (xx.x%)	xx (xx.x%)
3 - Moderate	xx (xx.x%)	xx (xx.x%)
4 - Severe	xx (xx.x%)	xx (xx.x%)
Week 2		
0 - Clear	xx.x%	xx.x%
1 - Almost Clear	xx.x%	xx.x%
2 - Mild	xx.x%	xx.x%
3 - Moderate	xx.x%	xx.x%
4 - Severe	xx.x%	xx.x%
Achieving Clear or Almost Clear		
Success	xx.x%	xx.x%
Failure	xx.x%	xx.x%

Note: Multiple imputation (MCMC) used to impute missing values. Percentages for Weeks 2, 4, 8, and 12 represent average values, obtained from averaging the summary statistics generated from each imputed dataset.

SOURCE: USERNAME/SPONSOR/PROJECT/JOBNAME (DATE,TIME)

Table 14.2.3.1.1: Summary of Investigator Global Assessment at Each Evaluation
(Intent-to-Treat Population)
(Page 2 of 4)

Investigator Global Assessment	E-BPO 5% Cream (N=xxx)	Vehicle Cream (N=xxx)
Week 4		
0 - Clear	xx.x%	xx.x%
1 - Almost Clear	xx.x%	xx.x%
2 - Mild	xx.x%	xx.x%
3 - Moderate	xx.x%	xx.x%
4 - Severe	xx.x%	xx.x%
 Achieving Clear or Almost Clear		
Success	xx.x%	xx.x%
Failure	xx.x%	xx.x%

Note: Multiple imputation (MCMC) used to impute missing values. Percentages for Weeks 2, 4, 8, and 12 represent average values, obtained from averaging the summary statistics generated from each imputed dataset.

SOURCE: USERNAME\SPONSOR\PROJECT\JOBNAME (DATE,TIME)

Table 14.2.3.1.1: Summary of Investigator Global Assessment at Each Evaluation
 (Intent-to-Treat Population)
 (Page 3 of 4)

Investigator Global Assessment	E-BPO 5% Cream (N=xxx)	Vehicle Cream (N=xxx)
Week 8		
0 - Clear	xx.x%	xx.x%
1 - Almost Clear	xx.x%	xx.x%
2 - Mild	xx.x%	xx.x%
3 - Moderate	xx.x%	xx.x%
4 - Severe	xx.x%	xx.x%
Achieving Clear or Almost Clear		
Success	xx.x%	xx.x%
Failure	xx.x%	xx.x%

Note: Multiple imputation (MCMC) used to impute missing values. Percentages for Weeks 2, 4, 8, and 12 represent average values, obtained from averaging the summary statistics generated from each imputed dataset.

SOURCE: USERNAME\SPONSOR\PROJECT\JOBNAME (DATE,TIME)

Table 14.2.3.1.1: Summary of Investigator Global Assessment at Each Evaluation
 (Intent-to-Treat Population)
 (Page 4 of 4)

Investigator Global Assessment	E-BPO 5% Cream (N=xxx)	Vehicle Cream (N=xxx)
Week 12		
0 - Clear	xx.x%	xx.x%
1 - Almost Clear	xx.x%	xx.x%
2 - Mild	xx.x%	xx.x%
3 - Moderate	xx.x%	xx.x%
4 - Severe	xx.x%	xx.x%
 Achieving Clear or Almost Clear		
Success	xx.x%	xx.x%
Failure	xx.x%	xx.x%

Note: Multiple imputation (MCMC) used to impute missing values. Percentages for Weeks 2, 4, 8, and 12 represent average values, obtained from averaging the summary statistics generated from each imputed dataset.

SOURCE: USERNAME\SPONSOR\PROJECT\JOBNAME (DATE,TIME)

